### **Response Per RECIST v1.1 Criteria Details**

Response status per RECIST v1.1 will also be assessed by the investigator using all lesions (target, non-target, and new [if present]) as part of each evaluation. Post-baseline evaluation CT or MRI imaging (per RECIST) is to be done in all participants at Screening and at Visit 7 of the first, second (if PD after first cycle), third, and last cycle. Participants with CR, PR, or SD in the injected tumor at Day 14 of the fifth or last cycle will have imaging on Day 56. There will be no PFS follow up beyond the treatment period. RECIST v1.1 results will be assessed by the investigator

and entered into applicable eCRF pages, including separate assessment of response for overall, target lesions, and non-target lesions.

### **Secondary Efficacy Analyses**

All efficacy analyses are secondary, because all efficacy endpoints are secondary.

Efficacy analyses will be conducted on the Efficacy Evaluable Population (refer to section 4).

Regarding analyses, efficacy response results for injected tumors and overall (per RECIST v1.1) will be reported separately. Generally, though, unless otherwise specified, both ways of assessment will be analyzed in the same manner.

#### 6.2.2.1 Best Overall Response, Objective Response Rate and Durable Response Rate

##### **Best Overall Response**

Separately for injected tumors and overall (per RECIST v1.1), a participant's best overall response (BOR) is determined by the highest qualitative value assessed during the study for the following hierarchy of objective response results: CR > PR > SD > PD > NE. In order for a valid value of SD to be assigned, there must be evidence of stable disease for at least 6 weeks. If the minimum time for SD has not been met on the first assessment, the assignment of BOR will depend on subsequent response assessments. Participants which do not have follow up data after a first assessment of SD prior to the minimum time requirement will be considered as not evaluable (NE). BOR will be based on assessments collected after the first intratumoral injection until disease progression; assessments collected after the start of new anticancer treatment will not be considered. Confirmation of response will not be required for BOR. Participants who do not have any post-baseline results for response will be considered as not evaluable (NE).

Separately for injected tumors and overall (per RECIST v1.1), BOR will be summarized using the efficacy evaluable population.

Waterfall plots of BOR results for each criterion will be presented graphically using maximum percent reduction. Swimmer plots identifying participant response patterns over time will also be separately provided.

##### **Objective Response Rate**

Separately for injected tumors and overall (per RECIST v1.1), the objective response rate (ORR) is defined as the number of participants who exhibit a BOR response of CR or PR during the up to 5 cycles of treatment divided by the number of participants in the efficacy evaluable population.

Separately for injected tumors and overall (per RECIST v1.1), the ORR will be presented; corresponding two-sided 95% Clopper-Pearson exact confidence intervals (CIs) and the underlying number of participants will also be provided. The efficacy analysis of primary focus will be the analysis of ORR for injected tumors.

### **Durable Response Rate**

Separately for injected tumors and overall (per RECIST v1.1), the durable response rate will be determined via persistence of CR or PR for at least 28 days, with the corresponding response duration calculation, in days, as (the earliest date of PD or death for any cause - the date of first documentation of CR or PR + 1). Participants who do not have at least 28 days of data following BOR of CR or PR will be considered to not have had durable response. Participants who discontinue prior to being evaluated for post-baseline tumor assessments will be considered as non-responders.

Separately for injected tumors and overall (per RECIST v1.1), the durable response rate will be presented; corresponding two-sided 95% Clopper-Pearson exact CIs will also be provided.

#### 6.2.2.2 Progression Free Survival

Separately for injected tumors and overall (per RECIST v1.1), PFS is defined as time from first intratumoral injection to date of progression or death for any cause, whichever occurs first, and is calculated, in months, as:

$$(\text{Date of first PD or death or censoring} - \text{date of first intratumoral injection} + 1) / 30.4375.$$

PFS derivation will not include tumor assessments collected after the end of study treatment as these are not planned for collection beyond the final cycle. Tumor assessments taken after switch to another anti-cancer therapy will be excluded from consideration.

The first date of PD would be the earliest date of any post-baseline response finding of progressive disease or death unless a participant is censored at an earlier date. If an assessment occurs over several days, the date of assessment as collected on the Response Assessments eCRF page will be used. If there are no adequate assessments for a participant, they will be censored on their first intratumoral injection date unless they died prior to having their first assessment (in which case the death would be treated as an event). If a participant receives subsequent anticancer therapy prior to documentation of progressive disease, PFS will be censored at the latest adequate assessment prior to additional therapy initiation. Otherwise, if a participant does not have documented progression within this PFS observation period (i.e., until any PFS event or censoring), the participant will be censored at the latest adequate assessment.

Separately for injected tumors and overall (per RECIST v1.1), PFS will be analyzed based on Kaplan-Meier methods; Kaplan-Meier curves will be plotted over time. The number and percentage of participants identified to have had a PFS event and those who were censored will be displayed. The median time to PFS and its corresponding 95% CI will also be produced.

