Subjects will be monitored for clinical safety events and changes in laboratory parameters throughout the study period. Subjects who experience a CR before the next cycle will not receive treatment but will continue to be followed during the study period. Subjects whose tumors achieve a CR but then recur during the study period may resume treatment with Ad/PNP-F-araAMP up to the maximum allowed 5 total cycles.

No formal follow-up visits are planned following the end of the study period (Day 56 of the last treatment cycle). However, the Investigational New Drug (IND) Sponsor may request follow-up information from the investigator on tumor status in subjects who have stable disease (SD), PR, or CR at completion of their study participation.

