9.2.5 Visit 7 (Days 14 ± 2)

- Record vital signs
- Examination of injected tumor site(s)
- For injected tumors palpable on physical examination, measurement with calipers or rulers, if possible
- Obtain blood specimen for hematology and chemistry parameters
- Assessment of tumor with CT scan or MRI on first, second (if PD after first cycle), third and last cycle.
- Obtain tumor biopsy, third cycle only.
- Record any AEs.
- Record any change in medications.

Following Visit 7 of the Last Cycle**9.2.6 Visit 8 (Day 28 ± 3 of the Last Cycle)**

- Examination of injected tumor site(s)
- Record vital signs
- Record any new or resolution of adverse events
- Record any change in medications
- For injected tumors palpable on physical examination, measurement with calipers or rulers, if possible
- Blood specimen for:
 - Hematology
 - Chemistry
 - Antibody to adenovirus (last cycle)

9.2.7 Visit 9 or Termination Visit (Day 56 ± 3 of the Last Cycle)

- Examination of injected tumor site(s)
- Record vital signs
- Record any new or resolution of adverse events
- Record any change in medications
- For injected tumors palpable on physical examination, measurement with calipers or rulers, if possible
- ECG
- Obtain blood specimen for:
 - Hematology
 - Chemistry

- CD4/CD8 T-cell counts
- Urine analysis
- MRI or CT scan for subjects who had CR, PR, or SD following last cycle

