Tumor response in the injected tumor(s) will be assessed by physical examination (tumor measurement using ruler or calipers, if tumor can be assessed by palpation) as well as by radiographic imaging (magnetic resonance imaging [MRI] or computed tomography [CT] scan). The same methods to assess the injected tumor(s) will be used at baseline and subsequent time points.

Participants will be assessed for safety frequently, including Day 14 of each cycle. Participants will be assessed 4 weeks after completion of the last or fifth cycle. During the study, participants will be monitored for AEs including signs of infection, and changes in hematological or chemistry parameters (see Appendix 2, Protocol Study Procedures Table).

Participants who withdraw early from treatment will be asked to complete Day 56 (of the last treatment cycle) study visit evaluations. The study schema is presented in Figure 1.

Figure 1: Study Design

DLT = Dose-limiting toxicity; IV = intravenously; PD = progressive disease, VP = viral particle;

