## 5 GENERAL CONSIDERATIONS

### 5.1 General Data Handling

All analyses will be conducted based on SAS 9.4 or higher.

Study data will be recorded in eCRFs for all screened and enrolled participants. The electronic data capture (EDC) vendor for this study is Allucent.

The protocol deviation data will be provided in spreadsheet format from the clinical trial management system (CTMS).

Analysis tables will be presented in aggregate (overall) for a specified population.

Data will be presented in by-participant data listings. Unless otherwise stated, all listings will be sorted by site ID, participant number, and assessment date (and time, if available).

Continuous data will be summarized by treatment group based on n, mean, median, standard deviation (STD), first quartile (Q1), third quartile (Q3), minimum value, and maximum value.

Categorical data will be summarized by treatment arm using frequency counts and percentages. Where applicable, 95% confidence intervals (CIs) will be provided. Unless otherwise stated, the denominator of percentages will be the number of participants in the population or the number with non-missing data.

- The number of missing values will be presented as a separate category with no percentage, but only if one or more participants are missing data.
- Counts of zero will be presented without percentages.

Relative to the number of digits after the decimal in the raw data, summary statistics will have the following number of digits after the decimal:

- Minimum and Maximum: same number of significant digits as the raw data
- Mean, Median, Q1, and Q3: one additional significant digit
- Standard Deviation (STD) or Standard Error (SE): two additional significant digits
- Percentages <100% will be reported to one decimal place and percentages of 100% will be reported with no decimal place.
- P-values will be reported to four decimal places. If the value is below 0.0001 it will be noted as < 0.0001; if the value is above 0.9999 it will be noted as > 0.9999.
- Summary statistics will not exceed four digits after the decimal. Some laboratory parameters or other data may require judicious deviation from this rule.

Unless otherwise noted, statistical inference will be based on a 2-sided 5% significance level.

All data up to the time of study completion/withdrawal from the study will be included in the analysis, regardless of duration of treatment.

Numbering for data displays will be based on ICH E3.

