## 6 ANALYSIS METHODS

### 6.1 Study Participant Data

#### 6.1.1 Participant Enrollment and Disposition

Participant enrollment and disposition data will be summarized for the enrolled population and listed. Enrollment and disposition summaries will include:

- Number of participants in each analysis population
- Number of participants who have discontinued the study
- Primary reason for early withdrawal/discontinuation from study
  - Progressive disease
  - Adverse Event
  - Withdrawal by Subject
  - Lost to follow-up
  - Protocol Specified Withdrawal Criterion Met
  - Protocol Violation
  - Physician Decision
  - Pregnancy
  - Non-Compliance with Study Drug
  - Non-Compliance with Study Schedule
  - Study Terminated by Sponsor
  - Site Terminated by Sponsor
  - Sponsor Request
  - Death
  - Other

- Is early withdrawal/discontinuation from study related to COVID-19?
- Time (months) on study
- Primary reason for early withdrawal/discontinuation from treatment
  - Progressive disease
  - Adverse Event
  - Withdrawal by Subject
  - Lost to follow-up
  - Protocol Specified Withdrawal Criterion Met
  - Protocol Violation
  - Physician Decision
  - Pregnancy
  - Non-Compliance with Study Drug
  - Non-Compliance with Study Schedule
  - Study Terminated by Sponsor
  - Site Terminated by Sponsor
  - Sponsor Request
  - Death
  - Other
- Is early withdrawal/discontinuation from treatment related to COVID-19?

Completion of treatment is defined as participants who have received at least three administrations of Ad/PNP and at least 1 infusion of F-araAMP prior to their withdrawal from the study.

Completion of the study is defined as any participant who completes one or more cycles (visits 1-7).

Participants who are discontinued from the study via the discretion of the investigator, or no longer receiving IP by other criteria specified in the protocol, will be considered to have completed the study if at least 1 cycle (visits 1-7) is completed.

Participants who withdraw from the study will be considered to have completed the study if at least 1 cycle (visits 1-7) is completed.

Participants contributing to each analysis population and final disposition status will be listed.

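### An undated cut-off in the SAP's PFS rule can drop the planned last-cycle Day 56 scan, and the durable-response formula counts a response already lost at the next scan

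*SAP*

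**What the plan says.** **Assessment window.** SAP 6.2.2.2 states: "PFS derivation will not include tumor assessments collected after the end of study treatment as these are not planned for collection beyond the final cycle". The SAP gives no date for the end of study treatment. In the RECIST details of SAP 6.2.2, participants with CR, PR or "SD in the injected tumor at Day 14 of the fifth or last cycle will have imaging on Day 56", and the same paragraph continues: "There will be no PFS follow up beyond the treatment period". Protocol 9.2.7 lists at Visit 9 "MRI or CT scan for subjects who had CR, PR, or SD following last cycle", and Protocol 9.3.5 puts that scan about 6 weeks after the previous one. SAP 5.1 says: "All data up to the time of study completion/withdrawal from the study will be included in the analysis, regardless of duration of treatment".

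TTR (SAP 6.2.2.3) takes over the PFS conventions, except that death censors. DOR (SAP 6.2.2.5) uses analogous censoring. For BOR, SAP 6.2.2.1 takes assessments until progression, while SAP 2 and the ORR definition refer to the up to five cycles of treatment.

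**Durability.** Protocol 10.3 and 12.6 require CR or PR to last at least 4 weeks. SAP 6.2.2.1 sets 28 days, counted from first CR or PR to the earlier of progression or death, plus 1. It also asks for 28 days of data after the response, but not that those data show response. Confirmation of response is not required.

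**The concern.** The reason given for the exclusion is that no later scans are planned, yet one is. Two programmers could code the sentence differently. If the scan is dropped, progression seen on Day 56 becomes censoring at an earlier scan in PFS and DOR, and a response first seen on Day 56 disappears from TTR. Whether such a response counts for ORR should also be explicit, because ORR for injected tumors is the efficacy endpoint of primary focus (SAP 6.2.2).

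The durability formula raises a different problem: the progression scan itself completes the interval that is meant to show persistence.

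Both matter because short response is the protocol's stated reason for repeat cycles. In Phase 1, 4 of 5 responding tumors progressed before the Day 56 follow-up (Protocol 2.3). With 10 evaluable participants, one reclassified participant moves the durable rate by 1/10, or 10 percentage points.

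**Working it through.** **Inputs.** Cycles start every 28 ± 3 days (Protocol 4.2). Scans are at Day 14 ± 2 of cycles 1, 3 and last, and at Day 56 ± 3 of the last cycle (both study procedures tables). The cycle 2 scan is conditional on PD after cycle 1 and is ignored unless cycle 2 is the last. Infusions end on Day 5. Months = days / 30.4375 (SAP 5.2).

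**The plan's own figures.** 56 − 14 = 42 days = 6 weeks, as Protocol 9.3.5 says. For the ORR rule (3 or more of 10; 10% versus 40%), exact binomial power is 0.8327 and alpha 0.0702, matching the stated 83% and 7%. Neither depends on this point.

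**Scan days.** Study day = 28 × (cycle − 1) + cycle day.

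| Last cycle | Scan days | Gaps (days) |
|---|---|---|
| 1 | 14, 56 | 42 |
| 2 | 14, 42, 84 | 28, 42 |
| 3 | 14, 70, 112 | 56, 42 |
| 4 | 14, 70, 98, 140 | 56, 28, 42 |
| 5 | 14, 70, 126, 168 | 56, 56, 42 |

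**(a) Last usable PFS scan, by reading of the end of study treatment.**

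| Reading | One cycle | Five cycles |
|---|---|---|
| Day 56 kept | day 56 (1.84 months) | day 168 (5.52 months) |
| End of last 28-day cycle | day 14 (0.46) | day 126 (4.14) |
| Last infusion (day 5; day 28 × 4 + 5 = 117) | none; censored at day 1 (0.03) | day 70 (2.30) |

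Day 56 is 56 − 5 = 51 days after the last infusion, so it follows the last dose on every reading.

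Take PR at last-cycle Day 14 and PD at Day 56. With Day 56 kept, DOR is an event at 56 − 14 + 1 = 43 days (1.41 months). On the end-of-cycle reading it is censored at 14 − 14 + 1 = 1 day (0.03 months). The durable-response formula still gives the same participant 43 days, hence durable.

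**(b) Durability score when PD follows at the next scan.** Score = gap + 1.

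| Gap | Nominal score | Window on gap | Score range |
|---|---|---|---|
| 28 | 29 | ± (3 + 2 + 2) | 22 to 36 |
| 42 | 43 | ± (2 + 3) | 38 to 48 |
| 56 | 57 | ± (6 + 2 + 2) | 47 to 67 |

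For overall response there are 11 pairs (42 days × 5, 56 × 4, 28 × 2). For injected tumors there are 9 (42 × 5, 56 × 2, 28 × 2): injected-tumor progression stops treatment, so PD at day 70 makes cycle 3 the last, and the day 14 to 70 pairs under last cycles 4 and 5 cannot occur. Every pair passes 28 days nominally. Only the two one-cycle pairs can fall short within visit windows.

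Illustration with assumed diameters: 50 mm at baseline, 34 mm at the first scan (−32%, PR), then 42 mm 56 days later (+23.5% from the smallest, PD; −16% from baseline). The score is 57 days and the response counts as durable.

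**The case against.** **On (a).** Protocol 4.2 says "No formal follow-up visits are planned following the end of the study period (Day 56 of the last treatment cycle"), Protocol 9.2.7 titles the visit as belonging to the last cycle, and the SAP's procedures table puts Visits 8 and 9 under the last cycle. On that labelling nothing is planned beyond the final cycle, the stated reason for the exclusion is true, and SAP 5.1 includes the scan. This is the stronger reading, and it stands.

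A reader might infer the opposite: that the SAP ends a cycle before Day 56 and so certainly discards the scan. SAP 3.1 says "Participants will be assessed 4 weeks after completion of the last or fifth cycle", and SAP 6.1.1 says "Completion of the study is defined as any participant who completes one or more cycles (visits 1-7"). The documents do not carry that inference. SAP 6.1.1 is a disposition rule whose visit range includes screening, and SAP 3.1 names neither a visit nor a scan. What remains is that the operative words exclude by the end of treatment, not the end of the cycle, and no date is attached.

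**On (b).** First response to progression or death is a common convention and is the interval used for DOR. The formula is therefore not an arithmetic error, and a reader who infers that it must be replaced goes too far. Requiring response at a later assessment is a stricter quantity: a participant could have a DOR of 57 days and fail it. Palpable tumors are also measured between scans, but SAP 6.2.2 ties formal response to the imaging time points, so the pairs above are unchanged. The convention suits a Kaplan-Meier duration. It does not by itself establish the yes/no statement that response persisted for 4 weeks.

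**Conclusion.** Both parts hold in limited form.

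(a) The PFS cut-off is ambiguous and conflicts on its face with a scan that both documents plan. The likelier reading loses nothing. The literal one ends usable imaging 42 days early (end of cycle), or after five cycles 168 − 70 = 98 days early (last infusion), and turns Day 56 progression into censoring.

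(b) On the nominal schedule, scan-detected progression at the next assessment cannot fail the durability test: 11 of 11 pairs for overall response and 9 of 9 for injected tumors.

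This rests on nominal 28-day cycles and scheduled scans. The Protocol Clarification Letter and CRF named in SAP 1 were not available and might date the term. The endpoints are secondary and descriptive, and the stated ORR power and alpha do not change. The point deserves correction but does not threaten the design.

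**What to change.** **(a)** Delete the exclusion in SAP 6.2.2.2. State that PFS, TTR and DOR use all tumor assessments through the last-cycle Day 56 visit and before any new anticancer therapy. Align the sentence in SAP 6.2.2 on PFS follow-up, and state that the same window applies to BOR and ORR. This is SAP wording only and uses scans already scheduled.

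**(b)** Keep the current durable rate and report a second one beside it: responders with an assessment at least 28 days after first CR/PR that still shows response, with no PD up to and including that assessment. Do not describe the current rate alone as showing 4-week persistence.

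For injected tumors, still showing response needs a baseline reference, whereas Protocol 9.3.4 and SAP 6.2.2 define PR against the smallest diameter. Assumed examples: 50, 30, 30 mm is 0% against the smallest but 40% below baseline; 50, 25, 31 mm is 38% below baseline but 24% above the smallest, so PD. The reference must be reconciled in both documents first, so this part is more than a SAP edit.

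**Cost of (b).** The second rate will usually be lower, and it is conservative for responses lost between day 28 and the next scan. Illustration, assuming exponential loss of response, no deaths, and S(t) = exp(−ln 2 × t / median):

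| Assumed median (days) | Current formula wrongly durable, 1 − S(28) | Second rate wrongly not durable, 42-day gap, S(28) − S(42) | Same, 56-day gap, S(28) − S(56) |
|---|---|---|---|
| 28 | 50% | 15% | 25% |
| 56 | 29% | 11% | 21% |
| 112 | 16% | 7% | 13% |

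The medians are assumptions, not figures from the documents. The gain narrows as responses lengthen, which is why both rates should be shown.

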#### 6.2.2.3 Time to Response

Separately for injected tumors and overall (per RECIST v1.1), TTR is defined as time from first intratumoral injection to date of first response value of CR or PR during the PFS observation period (i.e., until any PFS event or censoring), and is calculated, in months, as:

(Date of first response or censoring - date of first intratumoral injection + 1) / 30.4375.

TTR will be analyzed in the same manner as PFS, including the same censoring conventions with exception that date of death is used for censoring, not as an event).

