Subjects will receive a total of 2×10^{11} VP Ad/PNP per injection (3 injections per cycle) distributed across the injected tumors and volume of vector will vary dependent upon estimated tumor volume using the tumor's two dimensions measured by calipers as described in the Operating Procedure - Injection of Investigational Product into the Tumors of Human Subjects. For example, for a subject with 3 tumors of 1.5 ml, 3 ml, and 5 ml size each, 2×10^{11} VP Ad/PNP will be suspended in 3.5 mL and tumors injected with 0.5 mL, 1.0 mL, and 2.0 mL, respectively. If the tumor mass is very large or the total volume for all discreet tumors exceeds 16 ml, a portion of the tumor mass or certain discrete tumors will be selected by the physician and injected with 5 ml of Ad/PNP. The same tumors will be injected with each administration of 5 ml Ad/PNP.

Lesion Volume	Injection Volume
> 16 ml	5.0 mL
12 ml to 16 ml	4.0 mL
8 ml to 12 ml	3.0 mL
4 ml to 8 ml	2.0 mL
2 ml to 4 ml	1.0 mL
Less than 2 ml	0.5 ml

Using aseptic technique, the Ad/PNP solution will be injected percutaneously with injection at multiple sites within the tumor to achieve thorough infiltration. A subcutaneous injection of local anesthetic may be used, if desired.

Approximately 24 to 36 hours following the third administration of Ad/PNP into the tumor (Day 3), subjects will receive 25 mg/m^2 F-araAMP daily for 3 days. F-araAMP will be prepared and administered intravenously over approximately 30 minutes per the package insert. Subjects who do not receive all three administrations of Ad/PNP will not receive F-araAMP; all subjects will be assessed for safety at the scheduled study visits. Subjects who do not receive all three full doses of Ad/PNP may be eligible to receive subsequent doses of F-araAMP at the discretion of the investigator.

In this study, each 5-day course of treatment will commence every 28 days +/- 3 days and subjects will receive up to 5 cycles of Ad/PNP-F-araAMP. The 28-day interval complies with the recommended dosing schedule between courses of F-araAMP used to treat hematological malignancies. Treatment will be discontinued prior to 5 cycles in the event of injected tumor progression (and/or the investigator determines the patient may no longer stand to benefit from further

treatment) or if there is no tumor present for injection. In the event that treatment is discontinued, the subject should complete the Day 28 and Day 56 visits of the last treatment cycle.

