#### 6.2.2.5 Duration of Response

Separately for injected tumors and overall (per RECIST v1.1), for participants who have been identified as a responder (achieved an overall response of CR or PR during the PFS observation period, i.e., until any PFS event or censoring), duration of response (DOR) is defined as time from first documentation of CR or PR until disease progression or death for any cause, whichever occurs first, and is calculated, in months, as:

(Date of PD or death - date of first response + 1) / 30.4375.

Censoring algorithms analogous to those for PFS will be used for DOR. If sample size permits, DOR will be analyzed based on the Kaplan-Meier methods described for PFS.

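### Time to response is analysed by Kaplan-Meier with death (explicitly) and progression (by implication) censored, so the curve can overstate the share who responded

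*SAP*

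**What the plan says.** SAP 6.2.2.3 starts the TTR clock at the initial Ad/PNP dose and lets it run "to date of first response value of CR or PR during the PFS observation period (i.e., until any PFS event or censoring"). The formula takes either the date of first response or a censoring date; there is no third outcome. The analysis follows PFS, "including the same censoring conventions with exception that date of death is used for censoring, not as an event". Section 6.2.2.2 supplies the method carried over: Kaplan-Meier, a plotted curve, counts of events and censored participants, and a median with its interval ("The median time to PFS and its corresponding 95% CI will also be produced").

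The population is everyone evaluable: "Efficacy analyses will be conducted on the Efficacy Evaluable Population". Duration of response, in contrast, is restricted in SAP 6.2.2.5, "for participants who have been identified as a responder". TTR has no such restriction.

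Two further passages settle who can still respond. Under Best Overall Response, "BOR will be based on assessments collected after the first intratumoral injection until disease progression". Protocol 4.2 adds: "Treatment will be discontinued prior to 5 cycles in the event of injected tumor progression".

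The protocol also names Kaplan-Meier for TTR (Synopsis, Statistical Methods; section 12.6), but does not say how death or progression is to be handled.

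**The concern.** Kaplan-Meier treats a censored participant as someone who could still respond later, at the same rate as those who remain at risk. That is reasonable for a participant who starts another anticancer therapy or misses assessments. It is not reasonable for one who has died, or who has progressed without responding and whose later assessments the plan does not count. For these participants the chance of a counted response is zero. Progression and death are competing events, and censoring them hands their share of the probability to the participants still at risk.

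At stake is the TTR output, produced once for injected tumors and once for overall RECIST response. The curve can climb above the proportion who responded. The median can be printed as a finite time although fewer than half the population responded. Both would stand beside an ORR whose numerator is "divided by the number of participants in the efficacy evaluable population", and which shows otherwise.

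**Working it through.** **Inputs.**
- Evaluable participants: 10 (SAP 3.3).
- Planning values (SAP 3.3): alternative ORR 40%, null ORR 10%, success at 3 or more responders.
- Scans: Day 14 of cycles 1, 3 and last (SAP 6.2.2). With 28-day cycles and five cycles these are about Days 14, 2 x 28 + 14 = 70, and 4 x 28 + 14 = 126. The conditional cycle 2 scan is left out.
- Event times: assumed, since the documents give none.
- On tied days, responses are counted before censoring.

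**The plan's own figure.** The TTR section states none. The ORR rule that anchors the illustrations reproduces: P(3 or more of 10) is 0.8327 at a 40% rate and 0.0702 at 10%, matching the stated 83% power and 7% alpha.

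**How progression is handled.** The window closes at any PFS event and the formula offers only response or censoring, so a participant who progresses without response can only be censored. The last adequate assessment in that window is the one that shows progression, so censoring at the progression date or at the last adequate assessment gives the same time.

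**Formulas.** At each scan, with n at risk, e responses and c progressions or deaths:
- Kaplan-Meier as planned: S is multiplied by (1 - e/n); the reported curve is 1 - S.
- Cumulative incidence (Aalen-Johansen): add S* x e/n, where S* is the probability of having had neither a response nor a competing event before that scan.

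**Illustration 1, 4 responders.** Day 14: 2 responses, 3 progressions. Day 70: 2 responses, 2 progressions. One participant stays progression-free.
- At risk at Day 70: 10 - 2 - 3 = 5.
- S(70) = 8/10 x 3/5 = 0.48, so 1-KM = 52%.
- Cumulative incidence = 0.20 + 0.50 x 2/5 = 0.40, equal to 4/10.

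**Illustration 2, 3 responders.** Day 14: 1 response, 5 progressions. Day 70: 2 responses. Two participants stay progression-free.
- At risk at Day 70: 10 - 1 - 5 = 4.
- S(70) = 9/10 x 2/4 = 0.45, so 1-KM = 55%.
- Cumulative incidence = 0.10 + 0.40 x 2/4 = 0.30, equal to 3/10.

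In both, S falls below 0.5 at Day 70, so the printed median is 70/30.4375 = 2.3 months (2.2 if Day 28 of a cycle is also Day 1 of the next, which puts the scan at Day 68). Over the whole population no median exists, because only 40% or 30% responded.

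**Illustration 3, a milder 3-responder pattern.** As illustration 2, but with 4 progressions at Day 14. Five are at risk at Day 70; S(70) = 9/10 x 3/5 = 0.54; 1-KM = 46% and no median is reached.

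**No distortion.** If 4 respond and 6 progress at Day 14, 1-KM = 40%, the crude rate.

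**Sensitivity of illustration 1.** Let k of the three Day 14 exits be progression or death and the rest genuine censoring. Cumulative incidence is 0.2 + (1 - (2 + k)/10) x 2/5:

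| k | Cumulative incidence | Excess of 1-KM (52%) |
|---|---|---|
| 3 | 40% | 12 points |
| 2 | 44% | 8 points |
| 1 | 48% | 4 points |
| 0 | 52% | 0 points |

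**Range.** Enumerating all distinct patterns over the three scans (15 x 28 = 420 with 4 responders, 10 x 36 = 360 with 3), the final 1-KM runs from the crude rate (40% or 30%) to 100%. No probability is attached to any pattern.

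**The case against.** The strongest reply is that the output is not misleading in context. Nowhere does the SAP call 1-KM a response rate or ask for it at a landmark time, so the 52% or 55% would have to be read off the curve. Event and censoring counts are displayed, ORR appears on the full denominator with an exact interval, and swimmer plots and listings show each participant. The median also comes with a 95% CI. With log-log limits (an assumption; the SAP names no type) the upper limit of S(70) is about 78% in illustration 1 and 80% in illustration 2, so the median has no estimable upper limit. Kaplan-Meier for TTR is protocol-specified, and the endpoint is secondary. All of this stands, and it limits the harm. It does not make the median or curve a correct description of response in the population analysed.

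A second reply is that censoring at progression is only implied. That is true, but a programmer still has to choose a rule, and the explicit censoring of deaths creates the same problem on its own.

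A reader might infer that the planned method always flatters the treatment. That goes too far. The direction is fixed only for 1-KM against cumulative incidence. Against a responders-only median the order can reverse: in illustration 1 the responders fall at Days 14, 14, 70 and 70, a median of Day 42, earlier than the Kaplan-Meier Day 70.

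**Conclusion.** The TTR rule is wrong as written and worth correcting, but no decision depends on it. Compared with the cumulative incidence of response, 1-KM is equal or too high, never too low. It is too high whenever a non-responder is censored for progression or death before a later response. The illustrated excess is 12 points (52% against 40%), 25 points (55% against 30%) and 16 points (46% against 30%), with a finite median in the first two. These sizes rest on assumed event times and on reading progression as censored. The 100% end of the range is a possibility, not an expectation.

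A reader might infer that the efficacy conclusion is compromised. It is not: ORR, its Clopper-Pearson interval, the 3-of-10 rule and the safety criterion do not use TTR. Censoring for new anticancer therapy or missing assessments is also not at fault.

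One editorial point sits nearby. The protocol (Synopsis, 10.3, 12.6) gives OS the PFS wording, progression or death; SAP 2 and 6.2.2.4 use death only, while SAP 1.1 declares no changes. The programmed OS analysis is clear and no result changes. The March 2023 clarification letter cited in SAP 1 was not available and may already settle it. A reader might go further and infer that OS is biased by short follow-up. The documents do not establish that: the arrangements may be in the letter or the CRF, and SAP 3.5 ties the final analysis to completion of scheduled assessments or to termination by the sponsor.

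**What to change.** Replace the last sentence of SAP 6.2.2.3 by one of two options, which answer different questions:

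1. **Whole population.** Estimate TTR by a cumulative incidence function with progression and death as competing events, censoring only for new anticancer therapy, missing assessments or end of observation without an event. Report a median only if the function reaches 50%. This repairs the curve and median directly.
2. **Responders only.** Drop the whole-population curve and median, and report n, median, minimum and maximum TTR among participants with CR or PR, labelled as conditional on response. This says how quickly responders responded, not how many did, and it yields a median however few they are.

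List the change in SAP 1.1, since the protocol (Synopsis, Statistical Methods; section 12.6) names Kaplan-Meier for TTR.

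Editorial, unless the clarification letter already covers it: reconcile the protocol's OS wording with the SAP's, record this in SAP 1.1, and remove from SAP 6.2.2.4 the phrase that splits OS by injected-tumor and RECIST assessment, which has no meaning for death.

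The cost is one SAP sentence, entries in SAP 1.1, a small programming change (simpler under option 2) and, if still needed, a protocol erratum. No new data, visits or participant contact are required. It should be done before database lock, by which time SAP 1 requires the final version.
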